Study Phases Screening Study Treatment Follow-Up	
(1) Screening: Screening for eligibility and obtaining consent
 
(2) Pre-Intervention: Baseline data collected, including ICP monitoring every 5 minutes for 15 minutes prior to the intervention to insure patients are at a steady state as it pertains to cerebral pressures. Patients with minimal ICP variation will then have an esophageal balloon placed to measure transpulmonary pressure.
 
(3) Intervention: PEEP titrated to "optimal PEEP" based on P_{tp}
 
(4) Post-Intervention: Data collection five minutes after intervention.
 
(5) Subject Completion/Withdrawal: Ventilator management will be returned to the primary critical care team to determine PEEP going forward. In patients who continue on the titrated level of PEEP, safety data will be collected for an additional 24 hours.

Efficacy/Safety Evaluations	This study is will use endpoints of ICP, CPP, and MAP to assess the safety of PEEP titration by P_{tp} measurements via

esophageal balloon. Determination of safety will be made based on the lack of a clinically significant increase in ICP, decrease in CPP, or decrease in MAP. All patients will have continuous hemodynamic and oxygenation monitoring, in addition to ICP/ CPP monitoring, per NSICU protocol to monitor patient safety. In patients who continue on the titrated level of PEEP after the intervention (decision made by the primary critical care team), ICP, CPP, hemodynamic, and oxygenation data will be recorded for 24 hours after the intervention to evaluate for any possible adverse events, and this data will also be reported.

Statistical and Analytic Plan

The trial is an interrupted time-series design non-inferiority trial evaluating “optimal PEEP” as determined by an esophageal balloon compared to baseline standard PEEP management. The primary outcome will be intracranial pressure with a non-inferiority limit of 4 mm Hg, analyzed with a non-inferiority design. CPP and MAP are secondary outcomes with non-inferiority margin of 10 mm Hg each.

DATA AND SAFETY MONITORING PLAN

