2.1 Primary Objective

To determine that titration of PEEP to optimal PEEP does not result in clinically significant changes in ICP (defined as an increase in ICP > 4 mm Hg).

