2.2 Secondary Objectives

- a. To determine that titration of PEEP to “optimal PEEP” does not result in clinically significant changes in CPP (defined as an increase in CPP > 10 mm Hg).
- b. To determine that titration of PEEP to “optimal PEEP” does not result in clinically significant changes in MAP (defined as a decrease in MAP > 10 mm Hg).
- c. To report any possible adverse events after titration of PEEP.

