3.2 Study Duration, Enrollment and Number of Subjects

Enrollment will continue until 18 subjects have been enrolled who require an increase in PEEP of at least 5 cm H₂O (based on P_{tp} at the time of enrollment). Based on a prior study which found 29% of participants were within 5 cm H₂O of optimal PEEP at the time of enrollment (2), we expect we will need to measure esophageal pressures on approximately 25 patients to find 18 patients who require titration of PEEP. Based on expected enrollment of 2-4 participants per month, the trial is expected to complete enrollment within 12 months. Each patient’s participation will last 1 hour; for the few patients who remain on higher PEEP per the request of the team, safety monitoring will continue for an additional 24 hours.

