6.3 Statistical Methods

All endpoints will be described in term of means and standard deviation, with associated 95% confidence intervals, and median [Q1-Q3]

The change in ICP will be analyzed with a non-inferiority study: the ICP value after intervention will be considered equivalent to the ICP before intervention if the 95% upper bound of the change is lower than the non-inferiority margin of 4 mm Hg.

In a similar manner, the CPP and MAP values before and after intervention will be considered equivalent if the 95% lower bounds of the respective changes are higher than -10 mm Hg.

Should the 95% upper bounds of ICP be higher than 4, the effect of the intervention would be considered inconclusive. Similarly if the equivalence of CPP and MAP cannot be observed, the intervention will be reported inconclusive for these endpoints.

Adverse events will be reported.

By study design, all patients will be monitored in the ICU for the duration of the study and missing values are not expected. However, in the unlikely event that missing values would be present, the subjects will not be excluded and statistics will be calculated on all available data. The dataset for analysis will consist of all subjects regardless of protocol deviation, as an Intent-to-treat population.

Additional data points from the table above will be collected and tabulated using mean and standard deviation.

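### Section 6.3 gives no verdict for a margin shown to be exceeded: an interval wholly beyond the ICP, CPP or MAP margin is labelled inconclusive, the same as an imprecise one

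*Combined protocol and SAP*

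**What the plan says.** For the primary endpoint, section 6.3 sets the success rule against a margin of 4 mm Hg: "the ICP value after intervention will be considered equivalent to the ICP before intervention if the 95% upper bound of the change is lower". It then deals with failure: "Should the 95% upper bounds of ICP be higher than 4, the effect of the intervention would be considered inconclusive".

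For CPP and MAP the success rule is a 95% lower bound of the change above -10 mm Hg. Failure is again a single category: "if the equivalence of CPP and MAP cannot be observed, the intervention will be reported inconclusive for these endpoints".

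The purpose is safety. The synopsis (Efficacy/Safety Evaluations) says: "Determination of safety will be made based on the lack of a clinically significant increase in ICP, decrease in CPP, or decrease in MAP". Section 2.1 sets the aim of showing that titration "does not result in clinically significant changes in ICP (defined as an increase in ICP > 4 mm Hg").

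Section 6.3 also asks for means, SDs and 95% confidence intervals for all endpoints. It does not say whether the decision bound is one-sided or two-sided; section 6.4 sizes the trial on a one-sided 95% interval.

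**The concern.** A bound that fails to clear the margin can come from two different results. The interval may contain the margin, so the data are compatible with a mean change on either side of it; *inconclusive* is then the right word. Or the whole interval may lie beyond the margin, so the data show that the mean change exceeds the limit the protocol itself calls clinically significant. Section 6.3 gives both the same label.

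The plan can therefore conclude that the margin was respected, or that it does not know, but never that the margin was exceeded. In a trial whose objective is safety, that third result should have a prespecified conclusion. Without one, authors facing such a result must either report it as inconclusive or depart from the plan after seeing the data.

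**Working it through.** **1. Every interval position against the 6.3 rules (ICP).**

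| 95% interval for mean change | Upper bound against 4 | Verdict under 6.3 | What the data show |
|---|---|---|---|
| wholly below 4 | below | equivalent | margin respected |
| contains 4 | above | inconclusive | undecided |
| wholly above 4 | above | inconclusive | margin exceeded |

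Rows 2 and 3 share a verdict. CPP and MAP behave the same way at -10, with the lower bound deciding.

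**2. Search for the missing verdict elsewhere.** The synopsis bases safety on the absence of significant changes but names no negative conclusion. Section 6.1 contains a fragment about a mean increase above 4, with no decision attached. Section 7.2 reports significant changes as adverse events, which is a patient-level rule. None of these gives a conclusion on the endpoint.

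**3. The plan's own sample sizes.** Inputs from 6.4: one-sided 5%, power 80%; margin and SD 4 and 4.4 (ICP), 10 and 11.3 (CPP), 10 and 11.8 (MAP). The formula 2 × [SD × (1.645 + 0.842) / margin]² gives 14.96, 15.79 and 17.22, that is 15, 16 and 18, matching 6.4. This is a two-group formula, so it does not settle whether the stated SDs describe single measurements or before-after changes. I take them as SDs of change (assumption) and use SD × √2 (6.22 for ICP), the value for uncorrelated single measurements, as the less favourable case.

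**4. When an ICP interval lies wholly above 4, with 18 analysed.** df = 17, two-sided t = 2.110, SE = SD/√18.

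- SD 4.4: SE = 1.037; threshold 4 + 2.110 × 1.037 = 6.19.
- SD 6.22: SE = 1.467; threshold 4 + 2.110 × 1.467 = 7.09.

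Example at SD 4.4: an observed mean rise of 7 gives 7 ± 2.19, or 4.8 to 9.2. Section 6.3 calls this inconclusive.

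**5. Chance of that result** (noncentral t, 18 analysed):

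| True mean rise | SD 4.4 | SD 6.22 |
|---|---|---|
| 3 | 0.2% | 0.5% |
| 4 | 2.5% | 2.5% |
| 6 | 44% | 25% |
| 8 | 95% | 73% |

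For a true fall of 20 mm Hg, the chance of an interval wholly below -10 is 94% for CPP (SD 11.3) and 92% for MAP (SD 11.8). With the SDs multiplied by √2 it is 71% and 67%.

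**6. If everyone enrolled is analysed.** Section 3.2 says "Enrollment will continue until 18 subjects have been enrolled who require an increase in PEEP" of at least 5 cm H₂O, with about 25 enrolled in all. Section 6.3 says "The dataset for analysis will consist of all subjects regardless of protocol deviation, as an Intent-to-treat population". The documents give no effect for the other seven, so I bracket it by simulation at SD 4.4.

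- No PEEP change and no effect in the seven: 3% at a true rise of 6 and 27% at 8. At 8 the all-subject mean is 18 × 8 / 25 = 5.76 and the average lower limit is 3.4, so in 73% of such trials the interval is not wholly above 4.
- Smaller titrations with half the effect in the seven: 22% at 6 and 84% at 8.

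**The case against.** The strongest reply is that little depends on this. A one-sided non-inferiority test has two outcomes, and failing it is conventionally not proof of inferiority. The background (1.3) describes ICP increases in earlier small studies as small or absent, and for any true rise within the margin the missing category is reached in at most 2.5% of trials. Harm would also be visible. Section 6.3 reports the intervals. Sections 7.2 and 7.3 report individual changes beyond the thresholds as adverse events, with independent physician review within 72 hours and submission to the IRB if judged likely or definitely related. At a true rise of 8 and SD 4.4 (normal changes assumed), Φ((8 - 4)/4.4) = 0.82, so about 15 of 18 titrated patients would individually exceed 4 mm Hg.

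All of this stands as a limit on the consequences. It does not make the rule right. Section 6.3 is not silent: it expressly assigns a label, and for an interval wholly beyond the margin that label is wrong. Adverse-event reports are not a conclusion on the mean change.

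A reader might go further and infer that the plan could declare titration safe despite shown harm, or would conceal harm. The documents support neither. A failed bound never yields a favourable verdict, and the data would be reported. Nor do they give grounds for expecting large harm. The use of *equivalent* for a one-bound test is a matter of wording and adds no weight here.

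**Conclusion.** The point holds as a narrow fault in the decision rule. Under 6.3, a mean change shown to be beyond the protocol's own margin receives the conclusion meant for imprecise data, for all three endpoints. The fault follows from the text alone and depends on no numerical assumption.

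Its practical size does depend on assumptions: the SD of change, the analysis set, and the effect in patients with little or no titration. It is negligible when the true ICP rise is within the margin and becomes common only at rises well beyond it. It shrinks if untitrated or barely titrated patients are included in the mean. It should be corrected before analysis, but it does not threaten the validity of a favourable result.

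**What to change.** Rewrite the decision rule in 6.3 as three mutually exclusive outcomes for each endpoint:

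- **Non-inferior**: the one-sided 95% bound of the mean change clears the margin (ICP upper bound below 4; CPP and MAP lower bound above -10, as 6.3 now has it).
- **Margin exceeded**: the opposite confidence limit is itself beyond the margin (ICP lower limit above 4; CPP and MAP upper limit below -10, on the same direction).
- **Inconclusive**: anything else.

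State the confidence level of the opposite limit. One choice is the one-sided 95% level that 6.4 uses for safety. The other is the two-sided 95% limit, with an acknowledgement that it asks for stronger evidence of harm than of safety. At 18 analysed and SD 4.4, the first is met at observed rises above 4 + 1.740 × 1.037 = 5.80 and the second above 6.19, so rises between those values change category. The false-positive rate at a true rise of exactly 4 is 5% or 2.5% respectively.

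Before the CPP verdict is written, the direction must be reconciled. Section 2.2 aims to show that titration "does not result in clinically significant changes in CPP (defined as an increase in CPP > 10 mm Hg"), whereas the synopsis and 6.3 use a decrease. Section 7.2 relies on the same definitions for adverse-event reporting, so it is affected too.

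The cost is a few sentences in 6.3 and the reconciliation of 2.2. Sample size, measurements and data collection are unchanged.

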4.4 Post-Intervention

Measurements of ICP, CPP, and MAP will be repeated 5 minutes after the change in PEEP.

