6 STATISTICAL CONSIDERATION

6.1 Primary Endpoint

The primary endpoint is change in ICP 5 minutes after PEEP titration. the parameter representing mean increase during/after titration is > 4 (mm Hg) in the target population.

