6.4 Sample Size and Power

Based on a non-inferiority trial design using a one-sided 95% confidence interval, a power of 80%, a non-inferiority limit of 4 mm Hg for ICP, and a standard deviation of 4.4 mm Hg based on previously published data (11), the study will need 15 participants who require a change in PEEP based on esophageal balloon measurements. To evaluate our secondary goals, using a non-inferiority limit of 10 mm Hg for CPP and a standard deviation of 11.3, we would need 16 subjects, and using a non-inferiority limit of 10 mm Hg for MAP and a standard deviation of 11.8, we would need 18 subjects.

Since we estimate that 29% will not need a change in PEEP (2), we expect we will need to enroll 25 participants and obtain esophageal balloon pressure measurements in order to have 18 participants requiring changes in PEEP.

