7.2 Safety Monitoring

Data will be collected 5 minutes after the intervention, giving time for pressure equilibration from the ventilator and its effect on ICP, CPP, and MAP. Significant changes in these metrics, as defined above, will be reported as adverse events. At the conclusion of the intervention, PEEP management will be returned to the primary team. In patients whom they continue the “optimal PEEP” level, we will continue to evaluate for possible adverse events for an additional 24 hours, and this data will be reported. In addition to clinically significant changes in ICP, CPP, and MAP as defined above, additional adverse events that will be reported will include evidence of new barotrauma, change in pressor requirement, or change in HR to > 120 or < 50 .

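### The trial is sized on 18 subjects who need more PEEP, but the analysis set is everyone enrolled, and the extra subjects pull the result toward non-inferiority

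*Combined protocol and SAP*

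**What the plan says.** - **Enrolment (3.2).** "Enrollment will continue until 18 subjects have been enrolled who require an increase in PEEP of at least 5" cm H₂O. The expected total of about 25 rests on a cited trial: "Based on a prior study which found 29% of participants were within 5 cm" H₂O of optimal PEEP at entry.
- **Sample size (6.4).** For ICP, "the study will need 15 participants who require a change in PEEP based on esophageal balloon measurements"; the figures for CPP and MAP are 16 and 18. The total is explained by "Since we estimate that 29% will not need a change in PEEP (2), we expect we will need to enroll 25 participants".
- **Primary endpoint (6.1).** The tested quantity is described as "the parameter representing mean increase during/after titration is > 4 (mm Hg) in the target population". The eligibility criteria in 3.3 contain no criterion on PEEP need.
- **Analysis set (6.3).** "The dataset for analysis will consist of all subjects regardless of protocol deviation, as an Intent-to-treat population". Non-inferiority for ICP is declared when the 95% upper bound of the change is below 4 mm Hg. For CPP and MAP the lower bounds must lie above -10 mm Hg.
- **Timing (4.4).** "Measurements of ICP, CPP, and MAP will be repeated 5 minutes after the change in PEEP".

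No section defines a set of subjects who needed the increase, a per-protocol set or a sensitivity analysis.

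**The concern.** The trial asks whether raising PEEP to the P_tp target raises ICP by a clinically important amount. Subjects already near the target receive little or none of that exposure, so their expected change is smaller. Including them dilutes any real effect, and in a non-inferiority analysis dilution favours success. The intent-to-treat label gives no protection here. That principle preserves a randomised comparison, and this is a single-group before-and-after study.

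The sections also leave room for more than one reading. Section 4.4 times the measurement from a change in PEEP, which gives no clear time point for a subject who has none, so an analyst could argue for titrated subjects only. With no rule deciding between the sets, the choice could be made after the data are seen. At stake is the primary safety conclusion, and the CPP and MAP conclusions with it.

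**Working it through.** **1. Reproduce the plan's figures.** Inputs from 6.4: one-sided 5%, power 80%, no true change; margin and SD 4 and 4.4 (ICP), 10 and 11.3 (CPP), 10 and 11.8 (MAP). The formula n = 2 × [SD × (1.645 + 0.842) / margin]² (the per-arm size for two independent samples) gives:

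- ICP 14.96, so 15
- CPP 15.79, so 16
- MAP 17.22, so 18

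These match 6.4, which applies them to subjects requiring a PEEP change. For enrolment, 18 / (1 - 0.29) = 25.4, stated as 25. The low-need group is therefore 25 - 18 = 7, or 28% of those analysed.

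**2. Effect on the mean.** If the 18 rise by 4 mm Hg on average, the pooled mean is:

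- (18 × 4 + 7 × 0) / 25 = 2.88 mm Hg if the 7 do not change
- (18 × 4 + 7 × 2) / 25 = 3.44 mm Hg if the 7 rise by 2

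With no change in the 7, the pooled mean reaches the margin only when the 18 rise by 4 × 25 / 18 = 5.6 mm Hg.

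**3. Chance of declaring non-inferiority for ICP when the true mean rise in the 18 is 4 mm Hg.** Simulation of normal changes; success if the one-sided 95% t upper bound of the pooled mean is below 4. The documents do not identify 4.4 as the SD of within-patient change, so SDs of 3, 4.4 and 6.2 were used (6.2 = 4.4 × √2, two uncorrelated readings). Each range covers a low-need SD of either 2 or the same value as in the 18.

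| Analysed | SD 3 | SD 4.4 | SD 6.2 |
|---|---|---|---|
| 18 alone | 5% | 5% | 5% |
| 18 + 7 at zero change | 46-50% | 29-35% | 20-25% |
| 18 + 7 rising by 1 mm Hg | 33-36% | 21-26% | 15-19% |
| 18 + 7 rising by 2 mm Hg | 21-24% | 14-17% | 11-13% |

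**4. Number of low-need subjects.** Enrolment stops at the 18th qualifying subject, so the low-need count varies. Under a negative binomial with 71% qualifying, the mean is 7.4 and the 5th to 95th percentiles are 3 to 13. Averaged over that distribution at SD 4.4, the rate is 32-38% with zero change and 15-19% at +2 mm Hg; over all three SDs and rises of 0 to 2 it is 12-51%. With exactly 3 low-need subjects it is 7-18%. With 13 it is 18-90%.

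**5. Two-sided interval.** Section 6.3 does not say whether its bound is one-sided. If it comes from a two-sided 95% interval (nominal 2.5%), the rate with 7 low-need subjects is 6-35%.

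**6. CPP and MAP.** With a true fall of 10 mm Hg in the 18 and 7 low-need subjects (low-need SD 5 or equal to that of the 18):

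- CPP, SD 11.3: 28-34% if the 7 do not change, 14-17% if they fall by 5
- MAP, SD 11.8: 27-33% and 14-16%

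**The case against.** The strongest reply is that the inflated error arises only from a combination that no section states: pool everyone, then judge the answer against the 18. Each pure reading is coherent.

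- **Titrated only.** The 6.3 sentence may be meant only to bar exclusions for deviations. With the endpoint timed from the PEEP change, a subject with no change has no value to pool. This does not cover a subject given an increase below 5 cm H₂O, who has a value and is outside the 18 as 3.2 counts them.
- **All enrolled.** The synopsis and 1.2 say all patients are titrated, and 3.3 is a natural referent for the target population. The 5% then holds for the mean over all enrolled. Power is not the difficulty: if the stated SDs are SDs of change, an exact paired t calculation needs only 9, 10 and 11 subjects. But 3.2 and 6.4 were still built on a different population, and the plan does not acknowledge it.

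It is also fair that every simulated case sets the rise in the 18 at the margin and gives the low-need subjects a smaller one, so a rate above 5% is built in. The plan's background expects small rises or none. If the true rise in the 18 is below 4 mm Hg, declaring non-inferiority is correct. The simulations establish the direction firmly and the size only conditionally.

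Individual changes beyond the limits remain visible (7.2: "Significant changes in these metrics, as defined above, will be reported as adverse events") and go to independent review under 7.3. That limits the harm to individual detection but leaves the primary conclusion diluted.

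**Conclusion.** The concern holds. The mismatch between 6.3 on one side and 3.2 and 6.4 on the other needs no assumption: it is in the text, and nothing elsewhere resolves it. Relative to the population on which the trial was sized, following 6.3 as written makes a false non-inferiority conclusion more likely than the nominal 5% whenever low-need subjects respond less. At SD 4.4 with 7 such subjects, the rate is roughly 14% to 35%. That size depends on assumed low-need rises of 0 to 2 mm Hg, on 4.4 being the SD of within-patient change, and on a true rise at the margin. Because it bears on the primary safety conclusion, it should be settled before any outcome data are examined.

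**What to change.** - **6.1 and 6.3.** Define the target population and the primary analysis set for ICP, CPP and MAP as subjects whose baseline P_tp, measured before titration, shows that they need the PEEP increase that counts toward the 18. Analyse them regardless of later deviations. Selection on a pre-titration measurement introduces no post-treatment selection. Base the non-inferiority conclusion on this set and report all enrolled subjects as supportive.
- **3.2 and 6.4.** Section 3.2 counts subjects needing an increase of at least 5 cm H₂O; 6.4 counts those needing any change, and describes as needing none the 29% whom 3.2 places within 5 cm H₂O of the target. Reconcile these so that one definition governs enrolment, sample size and analysis. Which definition is for the sponsor to decide.
- **Alternative.** If the mean over all enrolled subjects is intended, state that estimand, redo 6.4 for it, and pre-specify the analysis of the 18 alongside.

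**Cost.** Wording only, with no extra patients, since enrolment already runs until 18 such subjects are found. The ICP interval widens by about a fifth: the one-sided half-width at SD 4.4 is 1.740 × 4.4 / √18 = 1.8 mm Hg with 18, against 1.711 × 4.4 / √25 = 1.5 with 25. Power with 18 and no true change stays at 98% (SD 4.4) or 84% (SD 6.2) for ICP, 97% for CPP (SD 11.3) and 96% for MAP (SD 11.8).

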4.3 Intervention

PEEP will be increased on the ventilator to achieve a P_{tp} between 0 and +2 cm H₂O (“Optimal PEEP”).

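### A subject below the Ptp target at the 5-minute reading is still analysed as evidence at optimal PEEP, because no count or analysis set depends on the PEEP delivered

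*Combined protocol and SAP*

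**What the plan says.** - **Objective.** Section 2.1 states the claim to be shown: "To determine that titration of PEEP to optimal PEEP does not result in clinically significant changes in ICP", with a rise above 4 mm Hg as the threshold.
- **Exposure.** Section 4.3: "PEEP will be increased on the ventilator to achieve a" Ptp between 0 and +2 cm H2O.
- **Count.** Section 3.2: "Enrollment will continue until 18 subjects have been enrolled who require an increase in PEEP of at least 5 cm" H2O, judged from Ptp at enrolment. Section 6.4 uses the same basis, planning 25 enrolled "in order to have 18 participants requiring changes in PEEP". Neither section asks whether the increase was delivered.
- **Reading.** Under Section 4.4, ICP, CPP and MAP "will be repeated 5 minutes after the change in PEEP". The reading does not depend on the target having been reached or held.
- **Analysis set.** Section 6.3: "The dataset for analysis will consist of all subjects regardless of protocol deviation, as an Intent-to-treat population". For missing values, "the subjects will not be excluded and statistics will be calculated on all available data". There is no at-target or per-protocol set, no sensitivity analysis and no rule for incomplete titration.
- **Data held.** The Section 5 table records PEEP and Ptp before and after the intervention. Section 6.3 only tabulates such additional data points by mean and SD.

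**The concern.** An intent-to-treat set protects a randomised comparison. Here each subject is compared with his or her own baseline, so there is no such comparison to protect. The objective concerns titration to optimal PEEP. A subject who needed the increase but was below target at minute 5 has a valid reading, counts among the 18, and enters the mean as though exposed. If PEEP raises ICP, partial exposure generally pulls the mean change toward zero, and in a non-inferiority test that is the passing direction.

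Two neighbouring issues are separate. One is missing values: here the reading exists. The other is subjects who need no change: here the subject needed one.

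At stake is a safety conclusion about optimal PEEP that could rest partly on subjects who were not at it, with no pre-specified analysis to show whether that matters.

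**Working it through.** **1. The plan's own figures.** Section 6.4 gives margins of 4, 10 and 10 mm Hg, SDs of 4.4, 11.3 and 11.8, one-sided alpha 0.05 and 80% power. The formula 2 × [SD × (1.645 + 0.842) / margin]² gives 14.96, 15.79 and 17.22, which round up to the stated 15, 16 and 18. Also 18 / (1 − 0.29) = 25.4, against 25 stated. The sample-size arithmetic is not at issue.

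**2. Pass rule.** Section 6.3 passes ICP when mean change + t(0.95, n−1) × s / √n < 4. With n = 18 and s = 4.4, the second term is 1.740 × 4.4 / 4.243 = 1.80 mm Hg.

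**3. Effect of under-delivery.** Assume that the true mean rise at full titration is exactly 4 mm Hg, so that a pass is a false pass. Suppose k of 18 subjects show a fraction r of that rise. The mean becomes [4 × (18 − k) + 4 × r × k] / 18. For k = 4 and r = 0 it is 56 / 18 = 3.11. The false-pass probability follows from the non-central t distribution with 17 degrees of freedom and non-centrality (mean − 4) × √18 / 4.4.

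| k of 18 | Mean, r = 0.5 | False pass | Mean, r = 0 | False pass |
|---|---|---|---|---|
| 0 | 4.00 | 5.0% | 4.00 | 5.0% |
| 2 | 3.78 | 7.5% | 3.56 | 10.9% |
| 3 | 3.67 | 9.1% | 3.33 | 15.2% |
| 4 | 3.56 | 10.9% | 3.11 | 20.6% |

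Simulation with the k subjects drawn separately agrees:
- Half the effect, N(2, 4.4): about 7%, 9% and 10% for k = 2, 3 and 4.
- Back at baseline PEEP, SD 4.4: about 10%, 13% and 17%.
- Back at baseline PEEP, SD 1: about 11%, 15% and 21%.

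**4. Adding an at-target set, under-delivery unrelated to response.** When those at target must also pass, the false-pass rate returns to about 5%.

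**5. The same, when strong reactors are the ones stopped.** For illustration, draw full-titration changes from N(4, 4.4) and let every subject above a threshold be stopped and show half the rise.

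| Handling of stopped subjects | Threshold 8 mm Hg (about 3.3 of 18) | Threshold 10 mm Hg (about 1.6 of 18) |
|---|---|---|
| Kept, as in 6.3 | 27% | 12% |
| Excluded | 42% | 17% |
| Replaced until 18 are at target | about 50% | 18% |
| Both sets must pass | 27% | 12% |
| Value just before the reduction used | about 5% | about 5% |

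The last row assumes that this value shows the full rise. The thresholds only illustrate the mechanism; they are not in the plan and are not proposed as rules.

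**The case against.** The strongest objection is that the scenario is hypothetical. No section describes titration being cut short. The intervention is one bedside adjustment in a one-hour study, and patients with ICP above 20, CPP below 60 or unstable ICP are excluded. This stands as far as the rate is concerned: the size is an assumption. It does not supply the missing analysis rule, since Section 6.3 itself provides for deviations.

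A second objection is that an attempted-titration effect is a defensible safety target. Section 6.1 refers to the increase during or after titration, and Sections 7.2 and 7.3 report individual significant changes as adverse events with independent review. Reactors are therefore not wholly invisible. But Section 2.1 is worded as titration to optimal PEEP, and none of these sections adds a second analysis set.

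A third objection is that keeping everyone is safer than selecting on target reached. Where strong reactors are the ones stopped, this is right: excluding or replacing them makes the false-pass rate worse (step 5).

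A reader might infer that retaining under-exposed subjects can only move the mean toward zero, or that those stopped will be the ones who react badly. The documents support neither. A strong reactor stopped partway may still show an above-average rise, and the plan says nothing about who would be stopped.

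Finally, read literally, Section 6.3 also keeps the roughly 7 of 25 subjects expected to need no change. With zero mean change in them, the overall mean is 4 × 18 / 25 = 2.88 and the false-pass rate is about 34% with full delivery (n = 25, SD 4.4). That is a larger but separate question about who is analysed. The figures in this point are for the 18 alone.

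**Conclusion.** The point holds as a gap in the analysis plan. The count rests on PEEP required, the reading is unconditional, and the only analysis set ignores deviations, while the objective concerns titration to optimal PEEP. Under-delivery generally favours passing if PEEP raises ICP.

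The size is conditional: with 2 to 4 of 18 under-delivered, the false-pass rate rises from 5% to about 7-21%. This rests on n = 18, SD 4.4 for the change, a true rise exactly at the margin and a one-sided 95% bound. The documents give no rate of incomplete titration. They do not show that such cases will occur, and they do not support counting only at-target subjects toward the 18. The change is worth making before analysis, because a set chosen afterwards would be chosen with the data in view.

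**What to change.** - **Section 3.2.** Leave the enrolment count unchanged, and do not replace subjects who fail to reach target.
- **Section 6.3, sets.** Keep the set of all subjects with an attempted titration. Add a pre-specified set of those whose recorded PEEP was raised and whose recorded Ptp was at least 0, the lower end of the target, at the 5-minute reading. Using only the lower end avoids dropping subjects above +2, who are not under-exposed.
- **Section 6.3, rule.** Declare non-inferiority for ICP, CPP and MAP only if both sets meet the margin.
- **Reporting.** List each incomplete titration with achieved PEEP, Ptp and reason.
- **Sections 4.4 and 5.** The at-target set drops anyone stopped for a bad reaction. So record ICP, CPP and MAP from the existing continuous monitoring just before any PEEP reduction, and use those values for stopped subjects in the all-attempted set.

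**Cost.** The at-target set needs no new data. The pre-reduction value needs one added case report form field and time point, because Section 5 schedules no reading during titration; this is more than SAP wording. The pass rule becomes slightly harder to meet, and the at-target set is less precise: with 14 of 18 at target, the term added to the mean grows from 1.80 to 1.771 × 4.4 / √14 = 2.08 mm Hg. No clinical rule for stopping titration is proposed.
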